2.4 DETERMINATION OF SAMPLE SIZE

The required sample size of the modified intent-to-treat infected (mITTI) population is 264 patients (176 patients in the baloxavir marboxil group and 88 in the placebo group). It is assumed that the reverse transcriptase polymerase chain reaction (RT-PCR)–positive rate (tested in a central laboratory) will be 75% of the randomized population; hence, approximately 366 patients will be randomized to ensure an adequate number of patients in the mITTI population and to allow for a 4% dropout rate. The total number of randomized patients may change based on the percentage of patients who are RT-PCR positive during the study.

The total mITTI sample size of 264 patients provides at least 80% power using the log-rank Chi-Square test to detect a 31-hour difference in the time to clinical improvement (TTCl) between treatment groups under the following assumptions: median TTCl in the placebo plus NAI group is 94 hours, 840 hours follow-up (35 days), using an alpha of 5%, and the minimal detectable difference is 23 hours. The TTCl in the placebo plus NAI group of 94 hours was selected after consideration of the response rates observed in a blinded review of TTCl including data from 127 patients.

The study power is calculated based on the primary endpoint incorporating a group sequential design (GSD) using a beta spending function with non-binding rule, to allow for one futility interim, without increasing the overall experiment-wise error rate.

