6.1 DETERMINATION OF SAMPLE SIZE

Two new factors influenced the revised sample size: 1) the revised assumption for the placebo plus NAI control-arm TTCI following blinded data review (Section 6.1.1) and 2) the faster than anticipated enrollment rate. Integration of these two factors informed a sample size readjustment to approximately 366 randomized patients. Assuming that the RT-PCR-positive rate (tested in a central laboratory) will be 75% of the randomized population and a dropout rate of 4%, the modified intent-to-treat (influenza) infected (mITTI) population will be 264 patients (i.e., 176 patients in the baloxavir marboxil group and 88 in the placebo group). The total number of randomized patients may change based on the percentage of patients who are RT-PCR positive during the study.

The total mITTI sample size of 264 patients provides at least 80% power using the Logrank Chi-Square test to detect a 31-hour difference in TTCI between treatment groups under the following assumptions: median TTCI in the placebo plus NAI group is 94 hours, 840 hours follow-up (35 days) using 5% alpha. The minimal detectable difference is expected to be around 23 hours. The alteration of the TTCI in the placebo plus NAI group to 94 hours was selected after consideration of the response rates observed in a blinded review (see Section 6.1.1) of TTCI including data from 127 patients.

The increased sample size has the consequential benefit of a larger population for safety analysis of the combination and multiple dose regimen specifically tested in this study for the severely ill hospitalized patient group.

The study power is calculated based on the primary endpoint incorporating a group sequential design (GSD) using a beta spending function with non-binding rule, to allow for one futility interim, without increasing the overall experiment-wise error rate.

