2.5.1 Planned Interim Analyses

After approximately 65% of TTCl events, a formal unblinded non-binding futility interim analysis (IA) based on the TTCl will be performed on the mITTI population. Enrollment will continue during the IA conduct.

The IA will be conducted by an unblinded external statistical group (independent Data Coordinating Centre [iDCC]) and reviewed by the iDMC (also unblinded), while the Sponsor will remain blinded until the end of study. Interactions between the iDMC/iDCC and Sponsor will be carried out as specified in the iDMC Charter. The iDMC Charter details the pre-planned interim analysis and potential recommendations the iDMC can make to the Sponsor as a result of the analysis (e.g., stop the study for futility or continue the study).

The futility interim analysis will use a Lan-DeMets Pocock beta spending function. The TTCl will be compared between treatment groups using a log-rank test adjusting for the stratification factor applied at randomization (i.e. region, National early warning score 2 [NEWS2] score, and time from symptom onset to study treatment), if the assumption of proportional hazards holds.

If the p -values seen at the interim is above the calculated futility bound ($\sim p=0.077$), and the iDMC members agree, based on their expert opinion, that there is no clinically meaningful difference in the TTCl, the trial may be declared futile and recruitment will be stopped. The futility bound will be re-calculated based on the final percentage of events in the IA.

Should the proportional hazards assumption be violated, the Gehan Wilcoxon test will be used to analyze the data. If the p -value is above the calculated futility bound ($\sim p$ -value=0.077) and the iDMC members agree, based on their expert opinion, that there is no clinically meaningful difference in the TTCl, the trial may be declared futile and recruitment will be stopped.

As the interim analysis is non-binding, the iDMC may choose to continue the study despite the futility boundary being crossed if they determine that there appears to be some evidence of a treatment effect from their evaluation of all the available TTCl data.

The expected RT-PCR positive rate of 75% will be continuously monitored prior to the IA to ensure this RT-PCR positive rate assumption is correct. The timing of the IA will be adjusted accordingly.

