4.5 EFFICACY ANALYSIS

Efficacy analyses will be conducted for the mITTI population. Hypothesis tests will be two-sided at the 5% significance level, unless stated otherwise.

To manage the overall type I error, the primary and key secondary endpoints will be tested sequentially. The order of testing will be as follows:

- TTCl
- Response rates of the 6-point ordinal scale at Day 7
- Time to Clinical Response

If the primary efficacy analysis hypothesis test result is not statistically significant (i.e. $p > 0.05$), the hypothesis below that result in the hierarchical chain will be considered exploratory and no claims of statistical significance will be made. The same rules apply to the next endpoint in the chain.

4.5.1 **Primary Efficacy Endpoint**

The primary efficacy objective for this study is to evaluate the efficacy of baloxavir marboxil plus a SOC NAI, compared with matching placebo plus SOC NAI based on the following endpoint:

- TTCI (defined as time from treatment start to hospital discharge or time to NEWS2 ≤ 2 and maintained for 24 hours, whichever comes first)

TTCI is calculated as per [Table 3](#).

Table 3 TTCI Calculations

TTCI based on	TTCI (hours)
NEWS2 ≤ 2 for 24 hours	date time of initial NEWS2 assessment ≤ 2 - start treatment date time
NEWS2 ≤ 2 prior to discharge*	date time of initial NEWS2 assessment ≤ 2 - start treatment date time
Hospital discharge	date time of hospital discharge - start date time of treatment

*when a patient met the NEWS2 ≤ 2 and was discharged from hospital during the 24 hour period of stability confirmation, the time of achieving TTCI was defined as the initial time at which the NEWS2 ≤ 2 and not the time of hospital discharge.

NEWS2 (National early warning score 2) is the sum of the score of each of the following assessments, as described in [Appendix 4](#): respiration rate (per minute), oxygen saturation (SpO₂%) according to scale 1 or scale 2, supplemental oxygen or room air, systolic blood pressure (mmHg), pulse rate (bpm), consciousness level, temperature (°C).

Missing data for the calculation of the NEWS2 will not be imputed for the following reasons:

1. TTCI endpoint can be met through hospital discharge.
2. The physiological components of the NEWS2 can be highly heterogeneous in the study patient population and therefore the process of imputation would not be relevant.

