The TTCI will be compared between the baloxavir marboxil plus SOC NAI and matching placebo plus SOC NAI arms using the stratified log-rank test within three regions (i.e. North America, EMEA, ROW), NEWS2 score at baseline (≤ 7 , > 7), and time from symptom onset to study treatment (≤ 48 hours, > 48 hours) included as the stratification factors. The Kaplan Meier plot, median time to response, 95% CIs, and p-values will be presented.

The log-rank test is most appropriate when the assumption of proportional hazards is met. The proportional hazards assumption will be tested graphically using the log cumulative hazard plot by treatment group. The plots for each treatment group will be parallel if the proportional hazard assumption holds. Should the proportional hazards assumption be violated, the Gehan Wilcoxon test will be used to analyze the data.

The estimand is the difference in distributions between baloxavir marboxil plus SOC NAI and matching placebo plus SOC NAI arms in the mTTi for the TTCI using appropriate method, as described above. This absolute measure will be assessed over the duration of the study (35 days). The median TTCI for each treatment group and difference between treatment groups will be presented. Intercurrent events are those that occur after treatment initiation and either preclude observation of the variable or affect its interpretation. Intercurrent events, such as patients who are lost to follow-up, die or discontinue for any reason prior to achieving a clinical improvement or do not have a clinical improvement event, will be accounted for through censoring rules, as described in [Table 4](#) below.

Table 4 TTCI and Censoring

Event	Censor	Date and Time
Clinical improvement (based on NEWS2 \leq 2 for 24 hours)	No	vital signs assessment where NEWS2 \leq 2 at start of 24 hour period
Clinical improvement (based on NEWS2 \leq 2 prior to discharge)	No	first vital signs assessment where NEWS2 \leq 2 prior to discharge
Clinical improvement (based on hospital discharge)		
- hospital discharge and hospital re-admission within 24 hours) and discontinue study on same day	Yes	hospital discharge
- hospital discharge and hospital re-admission within 24 hours) and continue study	Yes	hospital discharge
- hospital discharge against medical advice (i.e. self-discharge)	Yes	hospital discharge
- all other hospital discharge	No	hospital discharge
Death prior to achieving a clinical improvement	Yes	last vital signs assessment prior to death

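### The stated 80% power fits an unstratified log-rank test; the planned 12-stratum test has about 70–74% if the futility rule is always followed and about 80–81% if it is always overridden

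*SAP*

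**What the plan says.** **Power.** SAP 2.4 states that the mITTI sample "provides at least 80% power using the log-rank Chi-Square test to detect a 31-hour difference". Protocol 6.1 says the same: it "provides at least 80% power using the Logrank Chi-Square test". Both add that the power incorporates a group sequential design with one non-binding futility look. Neither mentions stratification.

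**Final test.** SAP 4.5.1 compares TTCI "using the stratified log-rank test within three regions", with NEWS2 (≤7, >7) and time from onset (≤48 h, >48 h) as further stratification factors. That is 3 × 2 × 2 = 12 cells. Protocol 6.4.1 and the synopsis name the same test. No rule for pooling sparse cells is given.

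**Interim test.** SAP 2.5.1 compares the arms at about 65% of events "using a log-rank test adjusting for the stratification factor applied at randomization". The futility bound is p of about 0.077 from a Lan-DeMets Pocock beta spending function. A stop also needs the iDMC to agree that there is no clinically meaningful difference, and the iDMC may continue past the bound.

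**The concern.** A stratified log-rank test compares patients only within their own cell. With 264/12 = 22 patients per cell on average, about 7 of them on placebo (and about 14 per cell in total at the interim), the last few patients in each cell form risk sets that are tiny or one-armed and carry almost no information. An unstratified test loses information in this way only once; a 12-cell test loses it twelve times. If the sample size ignored this, the stated power does not belong to the test that will be run, and the futility look will stop an effective drug more often than intended. Both key secondary endpoints are tested only after the primary succeeds, so they share the loss.

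**Working it through.** **Inputs**
- SAP 2.4: control median 94 h and a 31 h difference, so 63 h on active; 840 h follow-up; "176 patients in the baloxavir marboxil group and 88 in the placebo group"; an RT-PCR-positive rate that "will be 75% of the randomized population"; 4% dropout.
- SAP 4.5: "Hypothesis tests will be two-sided at the 5% significance level".
- SAP 2.5.1: interim at 65% of events, bound about 0.077.
- Assumed: 264 events (every mITTI patient has one). The plan gives no event count, and this is the most favourable case.

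**1. Reproduce the plan's figures without strata**
- Sample size: 366 × 0.75 × 0.96 = 263.5, or 264.
- Hazard ratio for improvement: 94/63 = 1.492; ln 1.492 = 0.400.
- Drift: 0.400 × √(264 × 2/3 × 1/3) = 0.400 × 7.66 = 3.065.
- Power with no interim: Φ(3.065 − 1.960) = 86.5%.
- Beta spent at 65%: 0.2 × ln(1 + (e − 1) × 0.65) = 0.150.
- With the look (correlation √0.65, bound 0.077 one-sided, final critical value 1.96 because the rule is non-binding): 80.3%.
- Solving the same design for exactly 80% gives 261.8 events and a one-sided bound of 0.0772.

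The power and the bound both come out of the unstratified formula, and the bound matches a one-sided p.

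**2. Rough size of the loss**

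A cell with n events loses about 1 + 1/2 + … + 1/n ≈ ln n + 0.58 events of information. Twelve cells of 22 lose 12 × (3.09 + 0.58) = 44 events, against ln 264 + 0.58 ≈ 6 unstratified. At the interim, twelve cells of about 14.3 lose 12 × (2.66 + 0.58) = 39 of 172, which is proportionately more. This is a heuristic and runs high: with permuted blocks, direct comparison of the test variances gives a net loss of about 31–32 events.

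**3. Simulation**

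The simulation used 6,000–10,000 trials per scenario. TTCI was exponential; 264/0.75 = 352 patients were randomised 2:1 in permuted blocks within cells and 264 kept as RT-PCR positive; follow-up stopped at 840 h. The interim fell at 65% of events, with a stop if one-sided p exceeded 0.077. The mix of patients across cells and the block size are not in the documents, so both were varied. Power in %:

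| Scenario | Unstratified, rule followed | 12 strata, rule followed | Unstratified, rule ignored | 12 strata, rule ignored |
|---|---|---|---|---|
| Equal cells | 79.2 | 71.6 | 85.9 | 80.7 |
| Unequal cells | 78.8 | 71.6 | 85.6 | 80.6 |
| Very unequal cells | 79.0 | 72.4 | 85.5 | 81.2 |
| Blocks of 3 | 77.3 | 70.8 | 84.4 | 79.7 |
| Simple randomisation | 78.6 | 70.1 | 85.2 | 79.2 |
| NEWS2 >7 slows improvement, HR 0.6 | 74.6–75.3 | 71.7–71.8 | 81.5–82.2 | 79.5–80.1 |
| Same, HR 0.4 | 66.5–66.9 | 70.8–72.5 | 74.1–74.4 | 79.2–81.0 |
| Same, HR 0.25 | 54.2–54.4 | 71.1–71.8 | 61.9–62.8 | 79.4–80.5 |
| 4% censored | 77.2 | 70.3 | 83.9 | 79.4 |
| 10% censored | 75.1 | 67.5 | 82.1 | 77.0 |

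Further runs of 4,000 trials gave 70–74% with the rule followed and 79–82% with it ignored for the 12-stratum test.

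**4. False futility stop under the planned effect**
- 12 strata: about 21–22%.
- Unstratified: about 17% with no prognostic effect, and about 19% with moderate effects (NEWS2 >7 HR 0.6, onset >48 h HR 0.85, region 0.9–1.15).

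Stratifying therefore adds about 2–5 points.

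**5. Scale**

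With the 12-stratum test and the rule followed, 80% power would need about 310–320 mITTI patients. At 0.75 × 0.96 = 0.72 that is 310/0.72 = 431 to 320/0.72 = 444 randomised, against 366.

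**The case against.** **The rule is non-binding.** A reader might infer that the plan simply delivers 72%. It does not: a stop needs both a p-value above the bound and iDMC agreement. At the bound (Z = 1.43, 172 events) the observed hazard ratio is about exp(1.43/6.18) = 1.26, a median shorter by 94 − 94/1.26 ≈ 19 h, which a committee might well call meaningful. So the range is about 72% to 81%, depending on how the rule is used. The lower end still matters, because SAP 2.4 says that its own 80% includes the futility design.

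**Stratification is sound.** A reader might infer that the 12-stratum test is a mistake and must be replaced. The documents do not support that. The test follows the randomisation factors, and its simulated one-sided type I error is 2.6%. TTCI is partly defined by NEWS2, so baseline NEWS2 may be strongly prognostic. With an HR of 0.4 the stratified test has about 71–74% with the rule followed, against about 65–68% unstratified. This stands in full. What is wrong is the power statement.

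**21% against 15% overstates the effect.** Accepted. The unstratified test itself stops falsely in about 17–19% of trials, so only part of the gap comes from stratifying.

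**The documents never call the power calculation unstratified.** True. It is inferred from the wording and from the reproduction of both the power and the bound.

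**The bound will be recalculated anyway.** SAP 2.5.1 says so, but only for the percentage of events at the interim, not for the test used.

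**Conclusion.** The concern holds as a mismatch between the stated power and the planned test. On the plan's effect size, with every patient having an event, the 12-stratum test has about 70–74% power if the futility rule is always followed and about 80–81% if it is always overridden. With the rule followed, type II error is about 28% rather than 20%. These figures assume exponential times and an unstated mix of patients across cells, but they barely move over the mixes, block sizes and prognostic strengths tried. Censoring lowers them further. Type I error is unaffected.

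**What to change.** **Needed.** In SAP 2.4 and Protocol 6.1, state the power for the 12-stratum log-rank test: about 72% with the futility rule followed and about 80–81% without it. In SAP 2.5.1, recalculate the futility bound for that test, say whether it is one- or two-sided, and give its operating characteristics, including the false-stop risk. Protocol 6.7.1 promises these in the SAP, which prints only the bound. The cost is a recalculation and wording; no patients and no new data.

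**Optional, before unblinding.** Use the treatment test from a Cox model with region, NEWS2 group and onset group as covariates, at both interim and final. Simulated power is about 78–79% with the rule followed and 85% without it, and one-sided type I error is 2.6%. Even so, it does not quite reach 80% with the rule followed. Stratifying by NEWS2 and onset only (4 cells) gives about 76%, but drops region, a randomisation factor. The Cox change would have to be recorded in SAP 3.3 and aligned with Protocol 6.4.1, the synopsis, the time-to-clinical-response analysis and the Gehan-Wilcoxon fallback. Its downside is the assumption that the three factors act proportionally on the hazard. Keeping the 12-stratum test is acceptable once its power is stated correctly.

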2.5 ANALYSIS TIMING

The primary study analysis will occur when the last patient has either withdrawn or completed Day 35 visit, and will be based on cleaned data for all patients up to and including this point.

2.5.1 Planned Interim Analyses

After approximately 65% of TTCl events, a formal unblinded non-binding futility interim analysis (IA) based on the TTCl will be performed on the mITTI population. Enrollment will continue during the IA conduct.

The IA will be conducted by an unblinded external statistical group (independent Data Coordinating Centre [iDCC]) and reviewed by the iDMC (also unblinded), while the Sponsor will remain blinded until the end of study. Interactions between the iDMC/iDCC and Sponsor will be carried out as specified in the iDMC Charter. The iDMC Charter details the pre-planned interim analysis and potential recommendations the iDMC can make to the Sponsor as a result of the analysis (e.g., stop the study for futility or continue the study).

The futility interim analysis will use a Lan-DeMets Pocock beta spending function. The TTCl will be compared between treatment groups using a log-rank test adjusting for the stratification factor applied at randomization (i.e. region, National early warning score 2 [NEWS2] score, and time from symptom onset to study treatment), if the assumption of proportional hazards holds.

If the p -values seen at the interim is above the calculated futility bound ($\sim p=0.077$), and the iDMC members agree, based on their expert opinion, that there is no clinically meaningful difference in the TTCl, the trial may be declared futile and recruitment will be stopped. The futility bound will be re-calculated based on the final percentage of events in the IA.

Should the proportional hazards assumption be violated, the Gehan Wilcoxon test will be used to analyze the data. If the p -value is above the calculated futility bound ($\sim p$ -value=0.077) and the iDMC members agree, based on their expert opinion, that there is no clinically meaningful difference in the TTCl, the trial may be declared futile and recruitment will be stopped.

As the interim analysis is non-binding, the iDMC may choose to continue the study despite the futility boundary being crossed if they determine that there appears to be some evidence of a treatment effect from their evaluation of all the available TTCl data.

The expected RT-PCR positive rate of 75% will be continuously monitored prior to the IA to ensure this RT-PCR positive rate assumption is correct. The timing of the IA will be adjusted accordingly.

The futility interim is non-binding on the Sponsor, and any deviation from the iDMC recommendation will be fully documented in the Clinical Study Report (CSR). If the study is stopped for futility, all recorded data up to that point will be reported for inclusion in a full study report.

3. STUDY CONDUCT

3.1 RANDOMIZATION, STRATIFICATION AND BLINDING

Following completion of screening and after all patient eligibility requirements are confirmed, patients will undergo randomization in a 2:1 ratio stratified by three regions (i.e., North America; Europe, Middle East, and Africa [EMEA]; and rest of world [ROW]), NEWS2 score (≤ 7 , > 7), and time from symptom onset to study treatment (≤ 48 hours, > 48 hours).

All patients will receive either baloxavir marboxil or its matching placebo. A permuted-block randomization method will be used to obtain an approximate 2:1 ratio between the active treatment group and the placebo group within each stratum. The placebo and active kits are filled and packaged to look identical.

Patients, investigators, and the Sponsor will be blinded to treatment assignment.

At study completion, stratification variables recorded in the Interactive Voice/Web Response System (IxRS) will be compared to the stratification variables recorded on the electronic Case Report Form (eCRF) to identify any mis-stratifications. These will be listed for all patients. If it is found that $> 10\%$ of mis-stratifications occurred, a sensitivity analysis will be carried out on the primary endpoint, using the eCRF stratification variables in the model.

3.2 SAFETY DATA MONITORING

An iDMC will evaluate safety during the study on a regular basis. All summaries and analyses by treatment group for the iDMC review are prepared by an external iDCC. Members of the iDMC are external to the Sponsor and follow a separate iDMC Charter that outlines their roles and responsibilities. Further details can be found in the iDMC charter.

